7. RESEARCH QUESTION AND OBJECTIVES

Primary Objectives:

To compare, through multivariate regression analyses:

- Two proxies of medication effectiveness (a validated criteria-based algorithm and a persistence-based measure)³ over 12 months of follow-up among RA patients treated with tofacitinib MR 11 mg once daily and tofacitinib IR 5 mg twice daily.
- 12-month proportion of RA patients who are persistent and adherent with tofacitinib MR 11 mg once daily and tofacitinib IR 5 mg twice daily.

Secondary Objectives:

To compare, through multivariate regression analyses:

- A persistence-based measure of effectiveness over 6 months of follow-up among RA patients treated with tofacitinib MR 11 mg once daily and tofacitinib IR 5 mg twice daily.
- A 6-month proportion of RA patients who are persistent and adherent with tofacitinib MR 11 mg once daily and tofacitinib IR 5 mg twice daily.

CCI

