Combination therapy, 90 days post-index (including index)	Baseline Clinical Characteristics	Combination therapy defined as first comedication with any csDMARD (Annex 2) within 90 days on or after the index date. Classify first csDMARD as methotrexate, leflunomide, hydroxychloroquine, sulfasalazine or other. If more than 1 csDMARD on same day, note methotrexate plus other or if not with methotrexate, just classify as >1 csDMARD other than methotrexate. Monotherapy defined as the complement to combination therapy.
Quan-Charlson comorbidity score, continuous, 12-month pre-index	Baseline Clinical Characteristics	A weighted scale of 17 co-morbidities (based on associated diagnosis codes on medical claims in the 12-months pre-index) presented as a summative score to evaluate co-morbid chronic illness burden.
Quan-Charlson comorbidity score, categorical 12-month pre-index	Baseline Clinical Characteristics	The continuous Quan-Charlson comorbidity score categorized into: 0, 1-2, 3-4, 5+ QCCI comorbidities (Annex 3). ^{4,9}
Opioid, non-steroidal anti-inflammatory drug (NSAID) use, dichotomous, 12-month pre-index	Baseline Clinical Characteristics	The use of weak and/or strong opioids and/or non-steroidal anti-inflammatory drug (NSAID) (Annex 2) during the 12-month pre-index periods.
Opioid, non-steroidal anti-inflammatory drug (NSAID) use, continuous 12 month pre-index	Baseline Clinical Characteristics	The number of pharmacy claims for weak and/or strong opioids and/or non-steroidal anti-inflammatory drug (NSAID) (Annex 2) during the 12-month pre-index periods.

Table 2. Variables Used in Analyses

Variable	Role	Operational definition
Pre-index corticosteroids, dichotomous	Baseline Clinical Characteristics	The use of oral corticosteroids (Annex 2) during the 12-month pre-index.
Pre-index corticosteroid total exposure/dose, continuous, 12-month pre-index	Baseline Clinical Characteristics	The total prednisone-equivalent dose of oral corticosteroids in the 12 months prior to index, defined as: the sum of prednisone equivalent dose (Strength*quantity/equivalence factor) of a filled corticosteroid. (Dose equivalent factors: Betamethasone=0.6, Dexamethasone=0.75; Methylprednisolone, Triamcinolone=4, Prednisone, Prednisolone=5; Hydrocortisone=20, Cortisone=25; Fludrocortisone=n/a).

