Proportion of Days Covered (PDC), 6 and 12 months post-index, continuous	Outcome (adherence)	
The PDC was defined as number of days covered by arrays for each fill or administration during the denominator periods of 180 and 360 days post-index. Patients with early refills will be allowed to stockpile medications up to a maximum of 14 days total for later use. PDC is capped at 1.0.

Proportion of Days Covered (PDC), 6 and 12 months post-index, dichotomous	Outcome (adherence)	
High adherence (PDC\geq0.8) vs. Low Adherence (PDC <0.8).

Table 2. Variables Used in Analyses

Variable	Role	Operational definition
Medication Effectiveness, algorithm defined, 12 months post-index, dichotomous	Outcome (effectiveness)	Patients who meet all 6 effectiveness criteria will be considered effectively treated. Patients who fail any one of the 6 criteria are considered not effectively treated.
High adherence criterion	Effectiveness criterion 1	High adherence criterion met if PDC ≥ 0.8 during the 12 month follow-up period.
Dose escalation criterion	Effectiveness criterion 2	No dose escalation criterion is met if no increases in index medication dose between index and 12 months after index. Dose increase threshold defined per Table 3 .
No treatment switch criterion	Effectiveness criterion 3	No treatment switch criterion is met if there is no use of an advanced therapy (Annex 2) other than index therapy during the 12 month follow-up period.
Addition of csDMARD criterion	Effectiveness criterion 4	No addition of csDMARD criterion is met if there are no claims for any csDMARD during the 1-year post-index for which there was not a claim during 1-year pre-index and/or 90 days post-index.

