Oral glucocorticoids criterion	Effectiveness criterion 5	The oral glucocorticoids criterion is met if a) For patients with no oral glucocorticoid prescriptions in the 6 months prior to index date, there is not more than 30 total days supply of oral glucocorticoids between 3-12 months post index; b) For patients with at least one claim for oral glucocorticoids during 6 months pre-index, oral glucocorticoid dose does not increase during months 6-12 post-index compared to the 6 months before the index date. Dose increase is defined as $\geq 20\%$ increase in prednisone equivalent dose (per above) for all glucocorticoid claims filled during the respective time periods. Note: Patients with more than one glucocorticoid injection during months 3-12 after index will be evaluated per the injection glucocorticoid criterion .
Injection glucocorticoid criterion	Effectiveness criterion 6	The injectable glucocorticoids criterion is met if patients have one or fewer glucocorticoid injections during months 3-12 after index date. Patients having one or more glucocorticoid injections on a single day are not considered to have failed the criterion.
Medication effectiveness, Duration of therapy (persistence), continuous, 12 month post-index	Outcome (effectiveness proxy)	The number of days between index date to the first of the following: the date of last prescription that is followed by a gap of 60 days without evidence of another advanced therapy prior to expiration of gap; the day before receipt of another advanced therapy; or the end of follow up period. A sensitivity analysis will be conducted for the Tofacitinib MR and IR comparison to include a switch in formulation as a criterion for discontinuation.

Table 3. Dose Escalation Criteria

Generic Name	Standard dosing schedule	Criteria for dose escalation for medication effectiveness
Tofacitinib (tofacitinib IR)	5 mg twice daily	At least 1 claim in the follow-up period with an average daily dose of at least 20 mg/day.
tofacitinib (tofacitinib MR)	11 mg once daily	At least 1 claim in the follow-up period with an average daily dose of at least 22 mg/day.

CCI

[REDACTED]

[REDACTED]

[REDACTED]

[REDACTED]

[REDACTED]

[REDACTED]

C
C
I

[REDACTED]

I

[REDACTED]

I

[REDACTED]

I

[REDACTED]

I

[REDACTED]

I

[REDACTED]

[REDACTED]

[REDACTED]

[REDACTED]

CCI

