8.9.3. Multivariate Analysis

To control for possible confounding of the relationship between the outcomes and independent variable of interest multivariable (logistic, generalized linear, and Cox) regression models will be evaluated as described in [Table 4](#).

The models will include insurance type, region, age, sex, prior advance therapies in variable length period (None, 1 and 2+) as covariates. The following variables will be evaluated for inclusion as a covariate and be included if differences between MR 11 mg QD and IR 5 mg BID at baseline with $p < 0.10$: 12-month pre-index use (% and means) of csDMARD, opioids, corticosteroids and presence of comorbidities including, cardiovascular disease, chronic obstructive pulmonary disease (COPD), asthma, kidney disease, depression, anxiety, liver disease, sleep disorders, hypertension, hyperlipidemia, Quan-Charlson comorbidity index and CIRAS scores, rheumatologist visit count during 1-year pre-index, disease duration, pre-index total costs, length of pre-index period, use of advanced therapy in 12 month pre-index and presence of csDMARD in 90 days post-index.

Generalized linear models (GLM) will be fit, using appropriate distributions and links for the nature of the data (eg, normally-distributed data with identity link, binary data and logit link). Point estimates, 95 percent confidence intervals, and p-values will be presented for contrasts; analysis of variance table will be presented to display the strength of the independent

variables, including point estimates and p-values. If there are problems with model fit, for example, failure to converge, transformation of data may be used in order to try a different distribution and link.

CCI [REDACTED]

[REDACTED]

[REDACTED]

[REDACTED]

[REDACTED]

[REDACTED]

[REDACTED]

[REDACTED]

[REDACTED]

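### Pre-index glucocorticoid injections are not among the readable baseline variables or covariates, although injections after index can by themselves fail the primary algorithm endpoint

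*Combined protocol and SAP*

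**What the plan says.** **The endpoint.** Section 7 makes effectiveness a primary objective, measured by "Two proxies of medication effectiveness (a validated criteria-based algorithm and a persistence-based measure"). Table 4 lists the algorithm-defined version as primary and dichotomous at 12 months, analysed by a generalized linear model. All six criteria must be met (Section 8.5, Table 2): "Patients who fail any one of the 6 criteria are considered not effectively treated".

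**The steroid criteria (Table 2).**
- Criterion 6: "The injectable glucocorticoids criterion is met if patients have one or fewer glucocorticoid injections during months 3-12 after index date". Several injections on one day do not count as a failure, so failing takes injections on more than one day. Nothing before index is consulted.
- Criterion 5 has two branches. The first opens "For patients with no oral glucocorticoid prescriptions in the 6 months prior to index date" and allows up to 30 days' supply in months 3-12. The second covers patients with an oral claim in those 6 months and fails them if their dose in months 6-12 is at least 20% above their own 6-month pre-index dose.

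**Baseline steroid variables (Table 2).** There are two readable rows: "The use of oral corticosteroids (Annex 2) during the 12-month pre-index", and "The total prednisone-equivalent dose of oral corticosteroids in the 12 months prior to index".

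**Covariates (Section 8.9.3).** Insurance type, region, age, sex and prior advanced therapies are always in the model. Steroids are a candidate only, under "12-month pre-index use (% and means) of csDMARD, opioids, corticosteroids and presence of comorbidities". Candidates will "be included if differences between MR 11 mg QD and IR 5 mg BID at baseline with" p below 0.10. The readable list contains no injection term and no 6-month oral term.

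**The concern.** Patients are not randomised to MR or IR, and Section 8.9.3 gives control of confounding as the reason for the models. Someone who received repeated injections before starting tofacitinib is plausibly more likely to receive them afterwards, and so to fail criterion 6 because of a pattern that was already there. If one cohort contains more such patients, it will look less effectively treated for a reason that predates the drug.

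Criterion 6 stands out among the criteria that look at added drugs. Criterion 4 disregards any csDMARD already claimed in the year before index. Criterion 5 takes account of the patient's own recent oral use. Criterion 6 has neither a baseline reference nor a matching covariate.

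A lesser issue concerns criterion 5. Its branch depends on oral use in the 6 months before index, while the covariates cover 12 months. A patient whose only oral fills fell in months 7-12 before index is a user in the model but is scored under the non-user branch.

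**Working it through.** **1. Route and window, side by side.**

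| Item | Route | Window | Pre-index reference |
|---|---|---|---|
| Table 2 baseline rows (any use; total dose) | oral | 12 months pre-index | – |
| Section 8.9.3 steroid covariate | not stated; matches the two oral rows | 12 months pre-index | – |
| Criterion 5, no oral use in prior 6 months | oral | months 3-12 post-index | 6-month status |
| Criterion 5, oral use in prior 6 months | oral | months 6-12 post-index | own 6-month dose |
| Criterion 6 | injection | months 3-12 post-index | none |

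The injection row has no baseline counterpart. CIRAS (Annex 4) contains no steroid item. The 6-month oral status is derived for criterion 5, but inside the outcome and not as a covariate.

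**2. Size of the possible bias.** The plan states no injection rate, cohort size, power or effect size, so there is no figure to reproduce and every rate below is an assumption. Suppose there is no formulation effect, criterion 6 failure is independent of the other five criteria, and no proxy adjustment is made. Let s be the probability of passing the other five criteria, q the share of a cohort with injection history, and f1 and f0 the criterion 6 failure rates with and without that history. Then

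P(effective) = s × (1 − [q × f1 + (1 − q) × f0]),

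and the spurious difference between cohorts is (imbalance in q) × (f1 − f0) × s.

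| Assumptions | 5-point imbalance | 10-point imbalance |
|---|---|---|
| Milder, low end: s=0.2, f1=0.2, f0=0.05 | 0.05×0.15×0.2 = 0.15 points | 0.10×0.15×0.2 = 0.3 points |
| Milder, high end: s=0.4, f1=0.4, f0=0.05 | 0.05×0.35×0.4 = 0.7 points | 0.10×0.35×0.4 = 1.4 points |
| Stronger, low end: s=0.3, f1=0.5, f0=0.1 | 0.05×0.4×0.3 = 0.6 points | 0.10×0.4×0.3 = 1.2 points |
| Stronger, high end: s=0.5, f1=0.7, f0=0.1 | 0.05×0.6×0.5 = 1.5 points | 0.10×0.6×0.5 = 3.0 points |

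The overall range is 0.15 to 3.0 points. On the odds ratio scale, the milder assumptions with history of 20% in one cohort and 25-30% in the other give spurious values of 0.94 to 0.99. For example, with s=0.4 and f1=0.4, the probabilities are 0.4×(1−0.12) = 0.352 and, at 30%, 0.4×(1−0.155) = 0.338, an odds ratio of 0.94. Equal history gives exactly 1.00.

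**3. Would adding the variable to the screened list be enough?** The probability that a true imbalance passes a two-sided test at 0.10, for assumed cohort sizes:

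| Per cohort | 20% vs 25% | 20% vs 30% |
|---|---|---|
| 200 | 33% | 75% |
| 500 | 60% | 98% |
| 1000 | 85% | about 100% |

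In small cohorts a 5-point imbalance would more often than not be screened out. The same rule applies to the oral variables, so even oral history may go unadjusted.

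**The case against.** The strongest reply has four parts.

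- **The model is not empty.** Section 8.9.3 lists oral steroids, opioids, CIRAS, rheumatologist visits and total pre-index costs, and those costs include paid injection claims. This stands, and a reader who inferred that nothing in the model could remove the difference would go too far. These are indirect proxies, however, and each must pass the p<0.10 screen.
- **Nothing suggests an imbalance.** Both cohorts receive the same drug, must have an RA code and a prior methotrexate claim, and Section 8.5 says the formulations cost the same. It is true that no imbalance is shown. None is ruled out either, and the plan would not measure it.
- **The source of a gap would be visible.** Table 4, footnote b, has the proportions failing each criterion described separately. That would reveal a criterion 6 gap between cohorts, but not whether it predated treatment.
- **The criterion 5 mismatch is minor.** A covariate need not copy an outcome's branching rule, the rule is the same in both cohorts, and users are compared with their own baseline. The 12-month use and dose variables contain the 6-month window. This largely stands: the mismatch is secondary, and its effect has not been quantified.

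A reader might also infer that a patient with an established injection pattern is bound to fail. The documents do not support that. Criterion 6 tolerates one injection day and starts at month 3, and even the stronger assumptions above leave 30-50% of such patients passing it.

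**Conclusion.** On the readable text, prior injection practice is not adjusted for as planned in the model for a primary endpoint that injections alone can fail. Under the assumed rates, a cohort imbalance of 5 to 10 points would shift the MR-IR contrast by roughly 0.2 to 3 percentage points, against the cohort with more prior injections. That range takes no credit for proxy adjustment and assumes criterion 6 failure is independent of the other criteria. With balanced history the bias is zero. The problem is conditional and modest, but cheap to close.

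It would be tempting to say that steroid history cannot be adjusted for. That is too strong. Oral history is partly covered by the 12-month variables, 6-month oral status is already derived for criterion 5, and criterion 6 itself shows that injections can be counted in these claims. Some rows of Table 2 and text after the covariate list in Section 8.9.3 are redacted, so a relevant variable or sensitivity analysis there cannot be excluded.

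**What to change.** 1. Add to Table 2 the number of days with a glucocorticoid injection in the 12 months before index, using the criterion 6 code list, and report it by cohort.
2. State in Section 8.9.3 that this variable enters the model for algorithm-defined effectiveness regardless of the p<0.10 screen.
3. As a secondary refinement, include in the same model the indicator of any oral glucocorticoid claim in the 6 months before index, already needed for criterion 5.
4. Leave the six criteria unchanged.

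The cost is one or two rows in Table 2, one sentence in Section 8.9.3 and one or two extra model parameters. The claims and codes are already needed for the outcome. If a redacted row already defines such a variable, only the sentence in Section 8.9.3 is needed.

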8.2.2. Exclusion Criteria

Patients meeting any of the following criteria will not be included in any study cohort:

1. Patients with claims for other conditions for which advanced therapies (bDMARD or Janus Kinase inhibitor (JAK)) are used during the one-year pre-index period or on the index date: ankylosing spondylitis, Crohn's disease, psoriasis, psoriatic arthritis, juvenile idiopathic arthritis or ulcerative colitis will be excluded from the study.

Table 1. Exclusionary Diagnosis

Disease	ICD-9 diagnosis code	ICD10 diagnosis code
Ankylosing Spondylitis	720.0x	M45.*
Crohn's Disease	555.xx	K50.*
Psoriasis	696.1x	L40.0*-L40.4*, L40.8*- L40.9*
Psoriatic Arthritis	696.0x	L40.5*
Ulcerative Colitis	556.xx	K51.*
Juvenile RA	714.3*	M08.*

ICD: International classification of diseases; RA = rheumatoid arthritis

2. Patients with evidence of the index medication during the one-year pre-index period. Patients will be allowed to have been treated with other advanced therapies defined as other bDMARDs or other JAK inhibitors (not tofacitinib) during the one-year pre-index period.
3. Patients with more than one advanced therapy prescription fill on the index date will be removed from the study, ie, a bDMARD and JAK inhibitor or more than one JAK inhibitor or two different tofacitinib formulations (ie, IR and MR), filled on the index date will be removed from the study.

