Length of variable length pre-index period, categorical	Baseline characteristic	Continuous variable length duration categorized into <13, 13-18, 19-24, 25-30,31-36 and >36 months.
CCI [REDACTED]	[REDACTED]	[REDACTED]
[REDACTED]	[REDACTED]	[REDACTED]
[REDACTED]	[REDACTED]	[REDACTED]
CCI [REDACTED]	[REDACTED]	[REDACTED]
[REDACTED]	[REDACTED]	[REDACTED]
CCI [REDACTED]	[REDACTED]	[REDACTED]
[REDACTED]	[REDACTED]	[REDACTED]
[REDACTED]	[REDACTED]	[REDACTED]

Table 2. Variables Used in Analyses

Variable	Role	Operational definition
CCI [REDACTED]	[REDACTED]	[REDACTED]
Treatment Persistent, 6 and 12 months post-index, dichotomous	Outcome (persistence)	
Patients who do not have a switch to another advanced therapy or discontinue tofacitinib (ie, 60-day gap between the run out of prior tofacitinib prescription and subsequent fill) over 6 and 12 month follow-up periods are characterized as persistent. The run out date is the prescription fill date + day supply – 1. For retail outpatient pharmacy prescription (RX) claims, the day supply will be utilized. There are no null tofacitinib days supply in dataset; however, claims with negative days supply or zero days supply will be excluded. Most tofacitinib prescriptions are for 30 days supply (86%) followed by 90 (12%) and 60 (~1%) days.
 
Patients with early refills will be allowed to accumulate a stockpile of the index medication of up to 14 days for later use.
 
A change in the formulation of active ingredient prescribed, eg, 5 mg BID vs 11 mg QD is not considered a switch for persistence endpoints in primary analyses.

Medication Possession Ratio (MPR), 6 and 12 months post-index, continuous	Outcome (adherence)	
The total days supply between the first and including the last tofacitinib prescription divided by the time between the first through and including last index therapy prescription days supply. Multiple prescriptions for the same treatment with the same fill date will be treated as one prescription with longest days supply; and for all prescriptions days supply will be capped at end of follow-up. MPR will be capped at 1.0 and will be reported at 6 months and 12 months.

Medication Possession Ratio (MPR), 6 and 12 months post-index, dichotomous	Outcome (adherence)	
High adherence (MPR\geq0.8) vs. Low Adherence (MPR <0.8).

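### Does a change between the IR and MR formulations fail criterion 3 of the algorithm effectiveness endpoint?

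*Combined protocol and SAP*

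**What the plan says.** Section 8.5, Table 2 builds the algorithm endpoint from six criteria and applies a strict rule: "Patients who fail any one of the 6 criteria are considered not effectively treated". Criterion 3, on treatment switch, is met if "there is no use of an advanced therapy (Annex 2) other than index therapy during the 12 month follow-up period". The term *index therapy* is not defined in the visible text, and Annex 2 refers the reader to code lists in the study folder.

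The explicit statement on formulation is in the persistence row of Table 2: a change of formulation, "eg, 5 mg BID vs 11 mg QD is not considered a switch for persistence endpoints in primary analyses". The duration-of-therapy row adds a sensitivity analysis in which a formulation switch does count as discontinuation.

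Two exclusions in Section 8.2.2 also bear on the term. Exclusion 2 allows earlier use of "other advanced therapies defined as other bDMARDs or other JAK inhibitors (not tofacitinib". Exclusion 3 begins "Patients with more than one advanced therapy prescription fill on the index date will be removed from the study" and gives as cases "a bDMARD and JAK inhibitor or more than one JAK inhibitor or two different tofacitinib formulations (ie, IR and MR", filled on the index date.

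Table 3, which feeds criterion 2 (dose escalation), has one row per formulation. The IR row reads "At least 1 claim in the follow-up period with an average daily dose of at least 20 mg/day" and the MR row "At least 1 claim in the follow-up period with an average daily dose of at least 22 mg/day".

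**The concern.** The two cohorts are defined by formulation, so the handling of formulation changes could affect the very contrast under study. The no-switch statement names persistence endpoints, and the algorithm endpoint is listed in Table 2 as an effectiveness outcome. Exclusion 3 can be read as treating IR and MR as two advanced therapies, and Section 8.3 assigns cohorts by the formulation first observed.

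On that reading, a patient on uninterrupted tofacitinib who only changes tablet would be persistent and yet fail the algorithm. Two programmers could then score the same patient differently on a primary endpoint. The per-criterion failure table promised in footnote b of Table 4 would mix such patients with those who moved to a different drug. Similar doubts can be raised about which row of Table 3 applies after a change, and about the MPR denominator, which also uses the term *index therapy*.

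**Working it through.** **Which reading does the text support?** There is no figure in the plan to reproduce, so the places are set side by side.

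- Section 8.2.1 defines the index event as the earliest pharmacy fill of tofacitinib, in whichever formulation.
- Exclusion 2 moves from the index medication straight to other advanced therapies, defined as "other advanced therapies defined as other bDMARDs or other JAK inhibitors (not tofacitinib". It concerns the pre-index year, but it shows how the protocol uses the words.
- Exclusion 3 counts fills, and lists two tofacitinib formulations as a case separate from more than one JAK inhibitor. If IR and MR were already two therapies, that case would be redundant. It is also a same-day rule at index and does not govern follow-up.
- The duration row ends treatment the day before another advanced therapy is received, then adds a sensitivity analysis to count a formulation switch. That addition is needed only if the default phrase does not already cover one. This row is itself labelled an effectiveness proxy, so role labels do not separate it from the algorithm.
- Criterion 1 uses PDC, whose numerator under Section 8.5 is tofacitinib supply. A formulation changer keeps credit for the new tablets in criterion 1, so failing the same patient in criterion 3 for taking them would make the composite inconsistent.

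All five fit *index therapy* = tofacitinib.

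**How far apart are the readings?** Let c be the share of a cohort that changes formulation and e the share of changers who otherwise meet all six criteria. Going from the tofacitinib reading to the formulation reading lowers the effective share by c × e in each cohort, so MR minus IR moves by

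c_IR × e_IR − c_MR × e_MR.

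All inputs here are assumed, with e equal in both cohorts.

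| c_IR | c_MR | e | Shift in MR − IR |
|---|---|---|---|
| 5% | 5% | 0.3 | 0.015 − 0.015 = 0 |
| 5% | 2% | 0.3 | 0.015 − 0.006 = +0.9 points |
| 10% | 2% | 0.2 | 0.020 − 0.004 = +1.6 points |
| 10% | 2% | 0.3 | 0.030 − 0.006 = +2.4 points |
| 10% | 2% | 0.4 | 0.040 − 0.008 = +3.2 points |
| 2% | 10% | 0.3 | 0.006 − 0.030 = −2.4 points |
| 2% | 10% | 0.4 | 0.008 − 0.040 = −3.2 points |

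If response is otherwise equal at 20% to 40% and changers respond like the rest, the 10%/2% case corresponds to odds ratios of 1.11 to 1.15. These figures measure the distance between two readings. They are not an error in the plan as naturally read.

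**Table 3 after a change.** The test is applied claim by claim, and each row names its formulation. A claim averaging 22 mg/day or more meets both thresholds and one below 20 mg/day meets neither, so row choice matters only from 20 to below 22 mg/day. A plain change from 2 × 5 = 10 mg/day to 11 mg/day triggers neither row. The case that could differ is an IR claim at 4 × 5 = 20 mg/day in an MR starter; judging each claim by the row for its own formulation settles it.

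**MPR.** Take IR fills on days 0 and 30, then MR fills on days 60, 120, 180, 240 and 300, each for 30 days.

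- Tofacitinib throughout: 7 × 30 = 210 days over 300 + 30 = 330 days, so 210/330 = 0.64.
- All tofacitinib in the numerator, starting formulation in the denominator: 210/(30 + 30) = 3.5, capped at 1.0.
- Starting formulation in both: 60/60 = 1.0.

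The second pairs mismatched quantities. The third contradicts Section 8.5, which puts tofacitinib supply in the numerator and runs the denominator from first to last prescription. Only the first fits the text.

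**The case for a change.** The best case for a change is that the authors foresaw formulation changes, wrote a rule for them, and limited it to persistence endpoints; a careful reader may take that limit as deliberate. The protocol itself calls a formulation change a switch in the duration row, and criterion 3 is about switching. The source algorithm cannot be assumed to help, since Section 8.11 says tofacitinib was approved for RA after the algorithm was developed. Settling the meaning before results are seen would also remove a choice on a primary endpoint at almost no cost.

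Part of this stands. Criterion 3 does not mention formulation, no visible sentence applies the no-switch rule to it, and the tofacitinib reading is an inference. But criterion 3 turns on use of a therapy other than the index therapy, and every place that gives content to that idea points to tofacitinib. The risk of divergent programming is also reduced by Section 8.10, which provides for a programming plan and verification by a second, independent programmer. Annex 2 or redacted text may already state the rule.

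**Conclusion.** No change to the plan follows. The gap is one undefined term that analysts would fill in the sense the rest of the protocol uses: index therapy means tofacitinib, so an IR-MR change does not fail criterion 3. Read that way, the algorithm, persistence and adherence endpoints treat a formulation changer alike, and cohorts, models and outcomes are unaffected. A clause in criterion 3 saying so would be a harmless courtesy, but no result depends on it. The Table 3 and MPR questions resolve from the existing text.

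The distance between the readings, -3.2 to +3.2 points across the scenarios above, rests entirely on assumed change rates and is zero when c × e is equal in the two cohorts. The conclusion rests on the visible text. It would need another look only if the Annex 2 list or redacted text assigned IR and MR to separate therapies for criterion 3.
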